#### Objectives and Endpoints

Objectives	Endpoints
Primary:	Primary:

To evaluate the PK profile of single IV dose of 900 mg PF-06823859 in healthy Chinese participants.

To determine the safety and tolerability of single IV dose of 900 mg PF-06823859 in healthy Chinese participants.

	

Serum PF-06823859 primary PK parameters, as permitted by data: <math>C_{max}</math>, <math>T_{max}</math>, <math>AUC_{14day}</math>, <math>AUC_{28day}</math>, <math>AUC_{inf}</math>, and <math>t_{1/2}</math>.

Assessments of AEs/SAEs including infusion site reactions and viral infections, vital signs, ECGs and laboratory tests.

Secondary:	Secondary:

To further evaluate the PK of PF-06823859

To evaluate the immunogenicity of PF-06823859.

	

Serum PF-06823859 PK parameters, as permitted by data: <math>C_{max}</math> (dn), <math>AUC_{last}</math>, <math>AUC_{last}</math> (dn), <math>AUC_{inf}</math> (dn), CL, <math>V_z</math>, and MRT.

Incidence of the development of ADA and Nab.

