### 1.3. Schedule of Activities

The SoA table provides an overview of the protocol visits and procedures. Refer to the [STUDY ASSESSMENTS AND PROCEDURES](#) section of the protocol for detailed information on each procedure and assessment required for compliance with the protocol.

The investigator may schedule visits (unplanned visits) in addition to those listed in the SoA table, in order to conduct evaluations or assessments required to protect the well-being of the participant.

Visit Identifier a Abbreviations used in this table may be found in Appendix 7 .	Screening	CRU Confinement										Follow-Up							ET			
		-28 to -2	-1	1					2	3	4	5	8	15	29	43	57	71		100	127	157
Days Relative to Day 1	-	-	-					-	-	-	-	±1	±1	±1	±3	±3	±3	±3	±3	±3	±3	-
Visit Window (days)	-	-	-					-	-	-	-	±1	±1	±1	±3	±3	±3	±3	±3	±3	±3	-
Hours After Dose			0 b	1	2	6	12	24	48	72	96	-	-	-	-	-	-	-	-	-	-	
Informed consent	X																					
Demography	X																					
CRU confinement		X	→	→	→	→	→	→	→	→	X											
Visit to the CRU	X	X									X	X	X	X	X	X	X	X	X	X	X	
Inclusion/exclusion criteria	X	X																				
Medical/medication history (update)	X	X																				
History of illicit drug, alcohol and tobacco use	X	X																				
Report prior or concomitant treatments	X	X	→	→	→	→	→	→	→	→	X	X	X	X	X	X	X	X	X	X	X	
Contraception check	X	X									X	X	X	X	X	X	X	X	X	X	X	
Physical exam (including height and weight at screening, only) c	X	X																			X	
Single 12-Lead ECG	X	X								X			X		X		X	X	X	X	X	
Supine blood pressure, pulse rate and temperature	X		X							X			X		X		X	X	X	X	X	
Chest radiograph d	X																				X	
Serious and nonserious AE monitoring	X	→	→	→	→	→	→	→	→	→	X	X	X	X	X	X	X	X	X	X	X	
Study intervention administration			X e																			
Safety laboratory (after ≥4-hour fast) including PT, INR, aPTT	X	X						X			X	X	X		X		X	X	X	X	X	
Viral surveillance (CMV, VZV, EBV, HHV6, HSV-1, HSV-2)	X										X		X		X					X	X	

Visit Identifier a Abbreviations used in this table may be found in Appendix 7 .	Screening	CRU Confinement										Follow-Up							ET		
		-28 to -2	-1	1					2	3	4	5	8	15	29	43	57	71		100	127
Days Relative to Day 1	-28 to -2	-1	1					2	3	4	5	8	15	29	43	57	71	100	127	157	-
Visit Window (days)	-	-	-					-	-	-	-	±1	±1	±1	±3	±3	±3	±3	±3	±3	-
Hours After Dose		0 b	1	2	6	12	24	48	72	96	-	-	-	-	-	-	-	-	-	-	

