##### 6.1.1. Administration

Intervention Name	PF-06823859 100 mg/mL	Placebo for PF-06823859
ARM Name (group of patients receiving a specific treatment, or no treatment)	Active	Placebo
Type	Biologic	Biologic
Dose Formulation	Solution for Injection	Solution for Injection
Unit Dose Strength(s)	100 mg/mL	0 mg/mL
Dosage Level(s)	900 mg	Placebo
Route of Administration	Intravenous	Intravenous
Use	Experimental	Placebo
IMP or NIMP	IMP	IMP
Sourcing	Provided by the sponsor.	Provided by the sponsor.
Packaging and Labeling	Study intervention will be provided in vials packaged in individual cartons. Each vial and carton will be	Study intervention will be provided in vials packaged in individual cartons. Each vial and carton will

	labeled as required per country requirement.	be labeled as required per country requirement.
--	--	---

Participants will receive study intervention at approximately 0800 hours on Day 1 (plus or minus 2 hours). Study intervention does not require fasting, but it should be noted that the safety laboratory test at Day -1 prior to the study intervention need a fast of at least 4 hours. Investigator site personnel will administer study intervention as a 60-minute intravenous infusion using a calibrated infusion pump. Study medication must not be administered as an IV push or bolus. The infusion rate, amount of volume infused, start and stop time of the infusion will be recorded. Time 0 is the time when the study drug infusion begins. The infusion will be on the opposite arm from PK sampling.

Administer study intervention according to the IP Manual.

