## 8. STUDY ASSESSMENTS AND PROCEDURES

The investigator (or an appropriate delegate at the investigator site) must obtain a signed and dated ICD before performing any study-specific procedures.

Study procedures and their timing are summarized in the [SoA](#). Protocol waivers or exemptions are not allowed.

Safety issues should be discussed with the sponsor immediately upon occurrence or awareness to determine whether the participant should continue or discontinue study intervention.

Adherence to the study design requirements, including those specified in the [SoA](#), is essential and required for study conduct.

All screening evaluations must be completed and reviewed to confirm that potential participants meet all eligibility criteria. The investigator will maintain a screening log to record details of all participants screened and to confirm eligibility or record reasons for screening failure, as applicable.

Participants will be screened within 28 days prior to administration of the study intervention to confirm that they meet the study population criteria for the study. If the time between screening and dosing exceeds 28 days as a result of unexpected delays (eg, delayed drug shipment), then participants do not require rescreening if the laboratory results obtained prior to first dose administration meet eligibility criteria, but some laboratory items may need to be retested if the screening period exceeds more than 30 days.

A participant who qualified for this protocol but did not enroll from an earlier cohort/group may be used in a subsequent cohort/group without rescreening, provided laboratory results obtained prior to the first dose administration meet eligibility criteria for this study, but some laboratory items may need to be retested if previous results are more than 30 days ago. In addition, other clinical assessments or specimen collections, eg, banked biospecimens, may be used without repeat collection, as appropriate.

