#### **8.2.7. Viral Surveillance**

Blood samples for possible analysis of CMV, EBV, HSV-1, HSV-2, VZV and HHV6 will be collected according to the times outlined in the [SoA](#).

*Note: Due to long turnaround time, the retrospective nature of these labs might make their reporting time quite delayed.*

In addition to time points specified, a blood sample for viral surveillance sample may also be taken at the time of an AE, as clinically appropriate.

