3.4. Baseline Variables

The baseline value for laboratory, 12-Lead ECG and vital signs is defined as the latest measurement prior to taking dose.

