6.5.5. Other Safety Data

Incidence of viral infections or change in baseline of viral loads (CMV, VZV, EBV, HHV6, and HSV-1/2) if they occur, will be summarized by treatment group.

Medical history and physical examination information, as applicable, collected during the course of the study will be considered source data and will not be required to be reported, unless otherwise noted. However, any untoward findings identified on physical examinations conducted during the active collection period will be captured as AEs, if those findings meet the definition of an AE.

All concomitant medications as well as non-drug treatments will be provided in the listings.

The safety analyses will be analyzed using the safety analysis set.

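### The only scheduled pre-dose viral sample is at screening, so silent conversions before dosing cannot be told from those after it

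*Protocol*

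**What the plan says.** Viral infections belong to the primary safety endpoint: "Assessments of AEs/SAEs including infusion site reactions and viral infections, vital signs, ECGs and laboratory tests" (Protocol, Objectives and Endpoints).

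In the schedule of activities (Protocol 1.3) the row "Viral surveillance (CMV, VZV, EBV, HHV6, HSV-1, HSV-2" has one mark before dosing, in the screening column (Day -28 to -2). The Day -1 and Day 1 pre-dose cells are empty. By cell position in the extracted table, the later marks are Day 5, Day 15, Day 43, Day 157 and early termination. The safety-laboratory row has marks at both screening and Day -1, and Protocol 6.1.1 confirms the second with its mention of "the safety laboratory test at Day -1 prior to the study intervention".

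On the length of the gap, Protocol section 8 says "Participants will be screened within 28 days prior to administration of the study intervention". It also lets an unexpected delay extend the gap beyond 28 days without full rescreening.

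On the analysis, SAP 3.4 says "The baseline value for laboratory, 12-Lead ECG and vital signs is defined as the latest measurement prior to taking dose". Protocol Appendix 2 (Table 2) lists viral surveillance among the safety laboratory tests, so this rule covers it. SAP 6.5.5 then summarises by treatment group "Incidence of viral infections or change in baseline of viral loads". It gives no case definition and no rule for dating a conversion.

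Protocol 8.2.7 describes the samples this way: "Blood samples for possible analysis of CMV, EBV, HSV-1, HSV-2, VZV and HHV6 will be collected". It warns that "the retrospective nature of these labs might make their reporting time quite delayed".

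**The concern.** Greater susceptibility to viral infection is the pharmacological risk the protocol itself names for blocking interferon beta (Protocol 2.3 and 4.2), and surveillance sampling is there to find events that cause no symptoms. For such events the only evidence of timing is the pair of samples on either side.

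With the last pre-dose sample at screening, that pair straddles the dose and may hold far more time before it than after. A participant negative at screening and positive at the first post-dose sample shows as a change from baseline in the assigned arm, whether the conversion came before or after the infusion. With 10 active and 2 placebo participants, the control arm cannot show how often this happens without drug.

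The early samples also matter for a planned use of the data. Protocol 4.1 and SAP 2.2 describe an unblinded sponsor review of safety data through Day 28. On the extracted schedule only the Day 5 and Day 15 viral samples fall inside that period.

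**Working it through.** The documents give no viral event rate, and Protocol 9.5 says the sample size has no statistical basis, so there is no stated figure to reproduce. The check has two parts.

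**1. Pre-dose share of the first detection interval**

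Inputs:
- k is the number of days from the baseline sample to dosing. Screening on Day -28 to Day -2 gives k = 28 down to 2 (there is no Day 0).
- d is the number of days from dosing to the first post-dose sample. Day 5 gives d = 4.
- Assumption: the conversion rate is constant over the interval.

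Formula: pre-dose share = k / (k + d).

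- Screening on Day -28: 28/32 = 87.5%
- Screening on Day -15: 15/19 = 78.9%
- Screening on Day -2: 2/6 = 33.3%
- Sample on Day -1: 1/5 = 20%
- Sample pre-dose on Day 1: 0/4 = 0%

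The extracted table may be shifted by a column. If the first post-dose sample is really Day 8 (d = 7), the current range is 2/9 = 22.2% to 28/35 = 80.0%, and a Day -1 sample gives 1/8 = 12.5%. The empty Day -1 cell does not depend on this reading, because neighbouring rows show marks at both screening and Day -1.

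**2. Chance that the problem arises at all**

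The rate p of silent conversion per participant over 28 days is not in the documents. The values below are illustrations only. For screening on Day -28, the chance of at least one pre-dose conversion among n participants is 1 - (1 - p)^n. With a Day -1 sample the daily rate 1 - (1 - p)^(1/28) replaces p.

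| Assumed p | 10 active, screening on Day -28 | 2 placebo, screening on Day -28 | 10 active, Day -1 sample |
|---|---|---|---|
| 1% | 9.6% | 2.0% | 0.4% |
| 2% | 18.3% | 4.0% | 0.7% |
| 5% | 40.1% | 9.8% | 1.8% |
| 10% | 65.1% | 19.0% | 3.7% |

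If there is exactly one such conversion, it falls in the active arm with probability 10/12 = 83%, from the allocation alone.

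**The case against.** Several points on the other side stand and limit the concern.

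- **No rule counts these events as on-drug.** A reader might infer that pre-dose conversions are counted as treatment effects. SAP 3.5.1 takes as treatment emergent only what occurs after treatment starts, and causality is judged case by case (Protocol Appendix 3). Appendix 3 does accept as an adverse event a condition first detected after dosing that may have been present earlier, but that does not assign it to the drug. The defect is that the schedule cannot separate the two cases.
- **Symptomatic infections are already dated.** Adverse events are collected from consent (Protocol 8.3.1), so an illness before dosing has a pre-dose onset. The exclusions for active infection in the 28 days before screening and for fever in the 7 days before dosing also help. Neither detects a silent conversion between screening and dosing.
- **Later visits are not affected in the same way.** A reader might apply the same formula to Day 15, Day 43 or Day 157. That ignores the intermediate samples: a participant negative at the first post-dose sample and positive later converted after the dose, if positivity persists.
- **The screening tube may be useful.** Exclusions 9 and 19 cover laboratory abnormalities that raise risk or affect interpretation, and 8.2.7 says only that results might be late. This argues against moving the tube, but not against adding one.
- **The optional wording in 8.2.7 is a separate matter.** A reader might infer that the assays are optional and that the count can only fall. Appendix 2 lists viral surveillance as required and Protocol 8.2.5 says all such tests must be done. An unassayed baseline tube could also raise the count, by making an existing infection look new.

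The study is small and descriptive, and both arms share the gap, so the comparison is not biased by design. Two placebo participants nevertheless give little protection.

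**Conclusion.** The concern holds for silent, laboratory-detected conversions and reactivations. The viral-load baseline is planned to be 2 to 28 days old at dosing, and a positive at the first post-dose sample cannot be dated to either side of the infusion. On a Day 5 first sample and a constant rate, 33% to 88% of that interval is pre-dose. A Day -1 sample would reduce this to 20%, which is not negligible; only a pre-dose sample on Day 1 brings it to zero.

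These are shares of an unknown number of events, which may be none. The result rests on the extracted table for the Day 5 visit, on the constant rate, and, for confining the ambiguity to the first post-dose sample, on positivity persisting between samples. The documents do not support saying that pre-dose conversions are attributed to the drug. This is a cheap improvement to the interpretability of one component of the primary safety endpoint, and it leaves the rest of the safety assessment untouched.

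**What to change.** 1. In Protocol 1.3, add a viral-surveillance sample at the existing Day -1 blood draw, or pre-dose on Day 1, and keep the screening sample.
2. In SAP 3.4, name the added sample as the viral baseline.
3. Separately, reword Protocol 8.2.7 to agree with Appendix 2, so that all scheduled viral samples are assayed.

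The cost is one small extra tube and assay per participant, plus one schedule cell and two sentences of text. Blood is already drawn on Day -1, so that option needs no new procedure. Keeping the screening tube preserves any result that could inform eligibility.

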## 2. INTRODUCTION

PF-06823859 is a potent, selective, humanized IgG1 neutralizing antibody directed against the human soluble cytokine IFN- $\beta$ , a member of the Type I IFN family of cytokines that is currently being developed for the treatment of DM with added potential for therapeutic benefit in SLE.

### 2.1. Study Rationale

The purpose of this study is to evaluate the single-dose PK, safety, and tolerability of PF-06823859 after single IV administration to healthy adult Chinese participants. The information of PK, safety, and tolerability in healthy Chinese participants is being collected to support future PF-06823859 clinical development as well as registration in China.

### 2.2. Background

DM is an acquired rare inflammatory disease classified as both a neuromuscular disease and an autoimmune disease. DM is characterized by a distinctive skin rash and muscle weakness or inflamed muscles. Symptoms can come on suddenly or gradually over time. It is thought that the inflammation resulting in cell damage is created when the immune system attacks healthy muscle tissue and blood vessels under the skin. DM is idiopathic; however, some individuals may have a genetic predisposition that is triggered by medications, viruses, bacteria, trauma, toxins, cancer or other illness. DM symptoms often wax and wane for no apparent reason and females are affected twice as often as males.

DM has no known cure and there are no widely approved treatments. Patients typically use a combination of drugs to seek relief for their inflammatory symptoms. Typically, the first line of treatment for the muscle disease is corticosteroids to address the inflammation as well as suppress the immune system. Other immunosuppressive drugs, notably azathioprine, methotrexate, mycophenolate mofetil and cyclophosphamide are used as subsequent lines of therapies in refractory cases or as steroid sparing agents. However, complications of long-term steroid and immunosuppressive therapies are well documented. Other novel approaches have emerged as potential treatment, including tacrolimus (broadly immunosuppressive drug developed for transplant use), intravenous immunoglobulin, and rituximab, following positive outcomes in some case studies. However, additional randomized controlled trials with these treatments are needed to guide clinical practice. Consequently, DM remains a disease with very high unmet medical need, and development of safe and effective therapies is warranted.

#### 2.2.1. Nonclinical Overview

In vitro assessments indicate that PF-06823859 is a potent inhibitor of IFN- $\beta$ /IFNAR signaling in human and cynomolgus monkey cells, and the data support the use of the cynomolgus monkey as a pharmacologically relevant-species for nonclinical toxicity studies. In addition, the nonclinical PK profiles of PF-06823859 in the cynomolgus monkey were typical for a human IgG mAb in monkeys. Furthermore, the nonclinical safety profile of PF-06823859 has been adequately characterized in vitro and in vivo in cynomolgus monkey to support progression into clinical trials up to 3 months in duration.

Detailed information concerning the nonclinical studies conducted with PF-06823859 can be found in the IB.

### 2.2.2. Clinical Overview

As of the protocol date, the Phase 1, randomized, double-blind, third-party open, placebo-controlled, dose escalating study to evaluate the safety, tolerability, pharmacokinetics and pharmacodynamics of single and multiple intravenous and subcutaneous doses of PF-06823859 in healthy participants (C0251001) has been completed. In addition, the Phase 2a, randomized, double-blind, placebo-controlled study to evaluate the efficacy, safety and tolerability of PF-06823859 in adult participants with DM (C0251002) is ongoing with no data available at this time.

Detailed information concerning the clinical studies conducted with PF-06823859 can be found in the IB.

CCI [REDACTED]

[REDACTED]

[REDACTED]

[REDACTED]

[REDACTED]

[REDACTED]

[REDACTED]

[figure not shown]
CCI [REDACTED]

[REDACTED]

CCI

CCI

### 2.3. Benefit/Risk Assessment

A single dose of PF-06823859 is not expected to provide any clinical benefit to healthy participants. This study is designed primarily to generate safety, tolerability, and PK data for further clinical development.

Nonclinical data to date ([Section 2.2](#)) has not identified any risk to reproductive organs in sexually mature cynomolgus monkeys, the pharmacologically relevant species. Given that an ePPND study will be conducted later in development, this protocol that allows enrollment of WOCBP has requirements for pregnancy testing (WOCBP only) and use of contraceptives to mitigate unintended exposures.

There is a theoretical risk that alterations in bone may occur based on published observations of osteopenia in mice genetically deficient in IFN- $\beta$ . The potential for bone effects was assessed in the 3-month GLP toxicity study in sexually mature cynomolgus monkeys, and there were no microscopic findings in bone, nor alterations in circulating bone-related

biomarkers. However, the potential for bone effects in developing/growing bones has not been specifically assessed in growing animals. This risk is considered to be low given the lack of observed effects in the GLP toxicity study as well as the limited duration of total exposure to PF-06823859 in this planned study. While appropriate risk mitigation has been employed, possible risks will be communicated to study participants in the ICD.

There is a potential risk of increased susceptibility to viral infections with IFN- $\beta$  blockade as with any antagonist of Type 1 interferon signaling (eg, anti-IFNAR1, anti-IFN- $\alpha$ , JAK inhibitors). Viral monitoring will be conducted as a precautionary measure to ensure participant safety. Furthermore, during the pandemic, study participants could be infected with the SARS-CoV-2 during study participation. This could lead to increased health risk for this participant and others in the study. Thus, participants must undergo COVID-19 specific assessments according to the [SoA](#).

The clinical impact of these potential risks will be minimized through the proposed standard, intensive, inpatient monitoring of the participants following administration of single, IV dose of the study intervention.

More detailed information about the known and expected benefits and risks and reasonably expected adverse events of PF-06823859 may be found in the IB, which is the SRSD for this study.

### 3. OBJECTIVES AND ENDPOINTS

Objectives	Endpoints
Primary:	Primary:

 
To evaluate the PK profile of single IV dose of 900 mg PF-06823859 in healthy Chinese participants.
 
To determine the safety and tolerability of single IV dose of 900 mg PF-06823859 in healthy Chinese participants.
 
	
 
Serum PF-06823859 primary PK parameters, as permitted by data: <math>C_{max}</math>, <math>T_{max}</math>, <math>AUC_{14day}</math>, <math>AUC_{28day}</math>, <math>AUC_{inf}</math>, and <math>t_{1/2}</math>,
 
Assessments of AEs/SAEs including infusion site reactions and viral infections, vital signs, ECGs and laboratory tests.
 

Secondary:	Secondary:

 
To further evaluate the PK of PF-06823859
 
To evaluate the immunogenicity of PF-06823859.
 
	
 
Serum PF-06823859 PK parameters, as permitted by data: <math>C_{max}</math> (dn), <math>AUC_{last}</math>, <math>AUC_{last}</math> (dn), <math>AUC_{inf}</math> (dn), CL, <math>V_z</math>, and MRT.
 
Incidence of the development of ADA and Nab.
 

